## 12. Study Population Characteristics

---

- ❖ Adults of  $\geq 18$  and  $\leq 90$  year old
- ❖ Both sexes
- ❖ Mild to moderate tear film dysfunction clinical diagnose
- ❖ 6 months recruiting
- ❖ Recruiting potential: once the research centers are opened it is estimated that, during the first month, inclusions will cover 75% of the total sample size.

### 12.1 Inclusion Criteria

---

- ❖  $\geq 18$  to  $\leq 90$  years old
- ❖ Both sexes
- ❖ Mild to moderate tear film dysfunction clinical diagnose
- ❖ Mild to moderate clinical stage of the disease
  - TBUT  $> 5$  sec. and  $< 10$  sec.
  - Schirmer:  $> 4$  mm and  $< 14$  mm
  - OSDI  $< 30$  points
  - Corneal staining  $<$  grade III on the Oxford scale
- ❖ Availability to go to each revision when indicated.

## 12.2 Exclusion Criteria

---

### 12.2.1 *General Criteria:*

1. Subjects with topical and/or systemic medication or mechanical devices that interfere determinedly on the results of the study (such as topical immunomodulators, punctal plugs, corticosteroids, preservative artificial tears, contact lenses).
2. Subjects (females) with active sexual life that do not use a contraceptive method.
3. Female subjects who are pregnant or lactating
4. Female subjects with a positive urine pregnancy test
5. Positive drug addictions\* (verbal interrogatory)
6. Subjects who have participated on any other research clinical trials on the last 40 days
7. Subjects legal or mentally disabled to give an informed consent for participating on this study
8. Subjects who can't comply with the appointments or with every protocol requirement.

\*Definition: repeated ingest of one or many psychoactive substances, until the consumer (named addict) is periodically or continuously intoxicated, showing a compulsive desire of consuming the preferred substance (or substances); he/she has a big difficulty to voluntarily interrupt or modify the substance consumption and is decided to obtain it anyhow. – Definition from the WHO\*

### 12.2.2 *Criteria related with ophthalmic ailments*

1. Serious tear film dysfunction syndrome
  - TBUT < 5 s
  - Schirmer: < 4 mm

- OSDI > 30 points
  - Corneal staining > grade III on the Oxford scale
2. Non perforated corneal ulcer
  3. Perforated corneal ulcer
  4. Autoimmune corneal ulcer
  5. Ocular surface scarring diseases
  6. Ocular surface or annexes metaplastic lesions
  7. Fibro vascular proliferation lesions on the conjunctival and/or corneal surface (i.e.: pterygium)
  8. Concomitant chronic inflammatory diseases on any ocular structure
  9. Acute or infectious inflammatory disease
  10. Corneal disease potentially requiring a treatment during the following 3 months
  11. Use of topical or systemic drug products classified as forbidden
  12. Ocular surgical procedures 3 months before the protocol inclusion
  13. Treatments or procedures indicated on the tear film dysfunction treatment, as punctal silicone plugs.
  14. Posterior segment diseases requiring a treatment or threatening the visual prognosis
  15. Retinal diseases potentially requiring treatment during the following 3 months
  16. History of penetrating keratoplasty.
  17. Soft or hard contact lenses use during the last month from inclusion day

### 12.2.3 Elimination criteria for the subject included on the study

1. Signs and symptoms evolving to serious tear film dysfunction syndrome detected on any treatment visit.
  - a. TBUT < 5 seconds
  - b. Peripheral or secondary leucoma to corneal scarring
  - c. Phlycten
  - d. Corneal keratinization
  - e. Epithelial squamous metaplasia
  - f. Corneal conjunctivalization
  - g. Corneal neovascularization
  - h. Corneal ulcers
  - i. Any secondary injury permanently reducing the visual acuity, as a consequence of the tear film dysfunction.
2. Added ocular surface diseases requiring a different treatment to PRO-087 or added treatments indicated for a new diagnose.
3. Opacities on ocular clear media (cornea, lens, vitreous body) avoiding to assess the anterior chamber or the posterior segment.
4. Decision of the subject
5. Difficulty to attend the follow-up appointments.
6. Added or self-prescribed non-authorized treatments
7. Herbal treatments affecting the course of the disease or producing other complications not related with the disease
8. Systemic diseases requiring an immunomodulator, immunosuppressing or biological treatments affecting any inflammatory cascade line.

9. Retinal diseases secondary to chronic-degenerating diseases requiring treatment to preserve the function and/or anatomy
10. Inflammatory retinal diseases
11. Uveitis presentation installation at any ocular uveal level
12. Clinical picture meaning an ophthalmic urgency requiring immediate treatment
13. Ocular diseases requiring surgical treatment
14. Ocular diseases requiring intraocular injections

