5. OSDI
6. Goblet cells population

It is considered that the drug in evaluation PRO-087 is effective for use in patients diagnosed with mild to moderate tear film dysfunction, if they exhibit the changes marked in parameters (14.1.2) by more than 5% of subjects in both eyes, in compliance with all visits and adherence to treatment at an 80% during the time of study assessment.

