#### 14.1.2 Efficacy Assessment Parameters

Parameters	Value
Best-corrected visual acuity	Increase of 1 line in the Snellen chart or 1 logarithmic point (logMAR)
Corneal depithelization	Percentage of the damaged epithelium of the ocular surface, reduction of staining according to the oxford scale.
Tear film break-up time	Increase in the residence of the teal film, measured in seconds. Increase of 30% from baseline or equal or more than 10 sec.
Schirmer test	Increase of more than 30%
Adverse events	Presence of adverse events modifying some of the abovementioned criteria or others, evaluated as serious.
OSDI	Reduction of 20% of the total score from the baseline score.
Goblet cells population	Increase of 20% from baseline

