#### 14.2.1 Tolerability Parameters

Parameters	Value
Burning	It should be recorded as absent on 95% of the evaluated subjects
Foreign body sensation	It should be recorded as absent on 95% of the evaluated subjects
Tearing	It should be recorded as absent on 95% of the evaluated subjects
Secretion	It should be recorded as absent on 95% of the evaluated subjects
Conjunctival hyperemia	
The following must be accomplished:
 
 
• Absent: <math>\geq 95.0\%</math>
 
• Mild: <math>\leq 5.0\%</math>
 
• Moderate: <math>\leq 2.5\%</math>
 
• Serious: <math>\leq 1.0\%</math>
 

Photophobia	
The following must be accomplished:
 
 
• Absent: <math>\geq 95.0\%</math>
 
• Mild: <math>\leq 5.0\%</math>
 
• Moderate: <math>\leq 2.5\%</math>
 
• Serious: <math>\leq 1.0\%</math>
 

Safety variables of the study drug PRO-087 will be evaluated in the visits indicated in the schedule, using the following parameters:

1. Best-corrected visual acuity
2. Intraocular pressure
3. Ocular surface
4. Anterior segment exploration
5. Posterior segment exploration
6. Tear film break-up time
7. Schirmer test
8. Corneal depithelization
9. Adverse events

It is considered that the drug in evaluation PRO-087 is tolerable for use in human beings, if there are not changes on the marked parameters (14.3.1) by more than 5% of subjects, in both eyes, in compliance with all visits and adherence to treatment at an  $\geq 80\%$  during the time of study assessment.

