#### 14.3.1 Safety Parameters

Parameters	Value
Best-corrected visual acuity	No change of 1 line in the Snellen chart or 1 logarithmic point (logMAR)
Intraocular pressure	Measurements below 7 mmHg and over 21 mmHg
Corneal depithelization	Percentage of the damaged epithelium of the ocular surface, reduction of staining according to the Oxford scale.
Anterior segment examination	Abnormalities on any of the comprised structures: Cornea, iris, pupil, iris-corneal angle and crystalline.
Posterior segment examination	Abnormalities on any of the comprised structures: Vitreous, retina, macula and optic nerve.
Tear film break-up time	Reduction of more than 20% over the baseline time.
Schirmer test	Reduction of more than 20%
Adverse events	Presence of adverse events modifying some of the abovementioned criteria or others evaluated as serious.
OSDI	Increase of the score of more than 10 points.

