## 15. Proposed statistical analysis.

---

The statistical analysis will be performed by an investigator blinded to the intervention groups.

The continuous quantitative variables will be presented by measures of central tendency and dispersion (mean, standard deviation and ranges). Nominal and ordinal qualitative variables will be introduced by means of frequencies and ratios.

The Kolmogorov-Smirnov test will be performed to know the normal or abnormal distribution of the results obtained in each study group.

Assuming there is a normal distribution of data, the intra-group differences will be determined by an ANOVA test for repeated measures, with the Pearson correlation coefficient, for the quantitative variables.

For qualitative variables the  $\chi^2$  (chi square) test will be used and in case the expected frequencies are less than 5 the Fisher's exact test will be used.

The differences between groups will be analyzed using the ANOVA test for variance analysis, with the Pearson correlation coefficient, for the qualitative variables.

For qualitative variables, contingency tables 2x2 will be used and the differences will be calculated with  $\chi^2$  (chi square) with Yates's correction and in case the expected frequencies are less than 5 the Fisher's exact test will be used.

The significance level will be of a 0.05 alpha value or less.

The final statistical analysis will include all the subjects that complete the visits listed in the activity chronogram.

Also, those who have been assigned with a treatment (intervention) and attend at least to 1 visit after the baseline will be included and analyzed until the moment they attended.

Those who do not attend at least 1 follow up visit will be excluded.

Those who do not complete the visits will be classified as population with intention to treat.

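### A TBUT below 5 s ends a subject's follow-up, and the section 14 verdicts, worded for all-visit subjects, can leave out those who worsened

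*Combined protocol and SAP*

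**What the plan says.** - **Entry (12.1).** Under "Mild to moderate clinical stage of the disease", TBUT must be above 5 s and below 10 s.
- **Elimination (12.2.3, item 1).** The trigger is "Signs and symptoms evolving to serious tear film dysfunction syndrome detected on any treatment visit". Item 1a lists TBUT under 5 s. It does not say whether one eye is enough.
- **Consequence (17.4).** The section on elimination opens by listing causes of withdrawal from the study. It asks the investigator to try to reach the patient for a final assessment. It names no study measurements for that contact and does not ask for the remaining visits. Data already available are retained for safety and labelled intention to treat.
- **Efficacy (14.1 and 14.1.2).** A TBUT response is "Increase of 30% from baseline or equal or more than 10 sec". The success rule applies to subjects "in compliance with all visits and adherence to treatment at an 80% during the time of study assessment".
- **Safety (paragraph after the 14.2.1 table, and 14.3.1).** A TBUT safety change is "Reduction of more than 20% over the baseline time". The drug passes "if there are not changes on the marked parameters (14.3.1) by more than 5% of subjects, in both eyes, in compliance with all visits" and with at least 80% adherence.
- **Analysis (15).** The final analysis takes completers. Subjects with at least one post-baseline visit "will be included and analyzed until the moment they attended". Then: "Those who do not complete the visits will be classified as population with intention to treat".
- **Schedule (9).** Impression cytology is done only at baseline and day 90.

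**The concern.** TBUT is both an efficacy and a safety variable, so item 1a ends follow-up on the value of a study outcome. A patient who enters just above 5 s can be removed by a very small fall. Everything scheduled after the trigger is then missing, including the only post-baseline cytology.

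The second problem is the count. Section 14 never mentions an eliminated subject. If its all-visits wording is taken literally, a subject removed at day 7, 30 or 60 is not counted. The patients removed this way are those whose TBUT worsened, so the omission favours the product. Section 17.4 points the other way by keeping their data for safety. Two analysts could take the same data and report different safety verdicts.

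**Working it through.** **1. Overlap of the two rules (from the documents alone).** A fall of more than 20% from baseline b gives TBUT below 0.8b. This is at or below 5 s whenever b ≤ 5/0.8 = 6.25 s. For baselines of 5-6.25 s, every 14.3.1 TBUT event therefore also meets item 1a. The reverse is not true: from b = 5.5 s, a reading of 4.9 s is a fall of 0.6/5.5 = 11%, which triggers item 1a but is not a safety event.

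**2. Plan figures used.** The SD of change is 1.1 s (13.1). The arm size is 80 × 1.2 = 96 (13.3). The plan gives no elimination rate, baseline TBUT distribution or within-subject correlation, so there is no plan figure to reproduce for the effect itself.

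**3. One-eye illustration.** Assumptions:
- baseline uniform on 5-10 s;
- change at days 7, 30, 60 and 90 normal with mean μ and SD 1.1 s, between-visit correlation ρ of 0, 0.5 or 0.8;
- elimination on any reading below 5 s at days 7-60;
- values observed up to and including the triggering visit.

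| μ | ρ | Eliminated | Fall >20%, all subjects (observed) | Fall >20%, all-visit subjects | Reduction |
|---|---|---|---|---|---|
| 0 | 0 | 19.6% | 29.2% | 21.0% | 28% |
| 0 | 0.5 | 16.0% | 21.7% | 14.5% | 33% |
| 0 | 0.8 | 13.2% | 16.1% | 10.0% | 38% |
| +1.0 s | 0 | 5.9% | 5.2% | 3.0% | 42% |
| +1.0 s | 0.5 | 4.9% | 4.0% | 2.3% | 43% |
| +1.0 s | 0.8 | 3.8% | 2.8% | 1.6% | 45% |

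- In patients per arm, the eliminated run from 96 × 0.038 ≈ 4 to 96 × 0.196 ≈ 19.
- With half the SD and μ = 0, elimination is 7-10%.
- Of subjects with an observed fall over 20%, 42-47% are among the eliminated.
- Of the eliminated, 37-44% (μ = 0) to 60-66% (μ = +1.0 s) have no observed fall over 20%.

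**4. Two-eye illustration, closer to the section 14 wording.** Assumptions: equal baselines in the two eyes; an event is a fall over 20% in both eyes at the same visit; ρ = 0.5; between-eye correlation 0.5 unless stated.

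| Case | Observed in everyone | All-visit subjects | Against 5% |
|---|---|---|---|
| SD 1.1, μ = 0, either eye triggers | 6.7% | 3.9% | verdict differs |
| SD 1.1, μ = 0, both eyes needed | 8.4% | 5.1% | both fail |
| SD 1.1, μ = +0.7 s, between-eye 0.5-0.9, both triggers | 1.3-4.6% | 0.6-2.7% | both pass |
| SD 0.55, μ = 0, both triggers | 0.2-0.3% | about 0.1% | both pass |

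At SD 1.1 s, the range of μ in which the two counts give different verdicts is 0.15-0.30 s wide. Its position moves between -0.30 and +0.75 s with the correlations and the trigger.

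**5. Efficacy (one eye, SD 1.1 s).** Day-90 TBUT response among all-visit subjects, against the eliminated counted as non-responders, is 12-13% against 10-11% at μ = 0, and 33-34% against 31-32% at μ = +1.0 s. All exceed 5%.

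**6. Between-arm mean (one eye, SD 1.1 s).** With true mean changes of 0 and +0.5 s, the day-90 difference among those remaining is 0.50, 0.464 and 0.452 s at ρ = 0, 0.5 and 0.8. The largest shift is 0.50 - 0.452 = 0.048 s.

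**The case against.** The strongest reply is that the plan already keeps what matters. Section 15 uses every subject with a post-baseline visit up to the last one attended. Section 17.4 retains withdrawn subjects' data for safety and names a population for them. It is also the more specific text on such subjects. The triggering TBUT is an observed value, and a trigger first met at day 90 loses no later visit. Removing a patient who progresses to serious disease is ordinary subject protection. This stands. A reader might infer that the worsening itself goes unrecorded, and the documents do not support that.

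A reader might also infer that an eliminated subject cannot satisfy the all-visits condition. That is only one reading: someone removed by protocol rule has not failed to comply with a visit. What survives is that section 14 does not say which reading applies, and its literal wording conflicts with 17.4.

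The figures are sensitive. With baselines concentrated in the middle of the range (Beta(3,3) on 5-10 s, also an assumption), one-eye elimination falls to 7-11% with no mean change and 1.4-2.1% with a 1.0 s rise. The two-eye case that crosses 5% assumes no mean improvement on an active lubricant. This limits the weight given to the point, not the reading of the text.

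Finally, 3.1 describes serious disease by OSDI, Oxford grade and TBUT together. Removal on one TBUT reading is thus the plain reading of item 1a but not the only one.

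**Conclusion.** The point holds with minor to moderate weight. Item 1a makes later data missing because of an outcome. The section 14 safety verdict, read literally, omits subjects who worsened and contradicts 17.4.

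The size depends on inputs the documents do not give. At SD 1.1 s with uniform baselines, the loss from the one-eye safety count is material in relative terms, but it decides the 5% verdict only in a narrow band that cannot be located from the documents.

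Three stronger conclusions are not supported:
- **That the comparison between arms is seriously biased.** The shift in step 6 is small.
- **That the TBUT efficacy verdict would reverse.** It did not in the one-eye cases run.
- **That every item-1a subject is a hidden safety event.** Step 3 shows that a large share of them never had an observed fall over 20%.

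**What to change.** **In 12.2.3 and 17.4.** Separate stopping study drug from leaving the study. A subject who meets item 1a may stop drug but keeps the remaining scheduled visits, with day-90 cytology if clinically acceptable, and is analysed in the randomised arm.

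**In section 14.** Remove the all-visits condition from the safety verdict, so that every observed TBUT fall over 20% counts, in line with 17.4. Report the efficacy verdict in all randomised subjects with a post-baseline visit. Whether eliminated subjects are also scored as non-responders is the sponsor's choice of estimand; it should be stated. While editing, say whether one eye or both trigger item 1a. The 5 s and 20% thresholds need not change.

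**Cost.** Protocol wording, plus visits already scheduled for about 4-19 of 96 subjects per arm in the one-eye illustration. Some data are collected off drug. A few subjects have a cytology after stopping drug, and 7.6 cites cell sampling among the reasons for the above-minimal risk class.

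The stated safety rate becomes less favourable. In the two-eye, either-eye-trigger example it rises from 3.9% to 6.7% when falls up to the trigger count. It reaches 9.5% if falls at the continued visits also count and changes off drug follow the same distribution. In one eye with a 1.0 s rise and ρ = 0.5, the corresponding rates are 2.3%, 4.0% and 4.5%.

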### 12.3 *Forbidden medications:*

Drug product group	Prototype	Route of administration	Washout period
Non steroid anti-inflammatory drugs	Ketorolac Bromfenac Diclofenac	Topical	2 weeks
Steroid anti-inflammatory drugs	Dexamethasone Prednisolone Fluorometholone	Topical and systemic	3 weeks
Prostaglandin analogues	Latanoprost Travaprost	Topical	4 weeks
Immunomodulators	Cyclosporine	Topical and systemic	2 months
Vasoconstrictors	Nafazoline	Topical	2 weeks
Agonists alpha 2	Brimonidine	Topical	3 weeks
Betablockers	Timolol, betaxolol	Topical	2 weeks
Preservative lubricants	Hirpomelose Sodium hyaluronate Propinylglycol	Topical	2 weeks

## 13. Sample size determination

---

The sample size was calculated according to the 3 major safety variables. The variable is considered the largest number of subjects obtained as the sample size required to meet the objectives of the study.

### 13.1 TBUT

The sample size was calculated according to the formula for continuous quantitative variables:

$$n=2 \left[ \frac{(Z_{\alpha} - Z_{1-\beta})(\delta)}{d} \right]^2$$

With a statistical confidence level of 95%, which corresponds to error type I, and is equal to 1.96, with a potency of 80% corresponding to error type II, and is equal to 0.84, a standard deviation for an increase in TBUT of 1.1 seconds was considered, with an expected difference of at least 0.15 seconds.

Based on the above, the result was 32 patients per group, which increased 20% in consideration of the losses, with a total of 39 patients per group, with a total study population of 116 subjects (232 eyes).

### 13.2 OSDI

The sample size was calculated according to the formula for continuous quantitative variables:

With a statistical confidence level of 95%, which corresponds to the error type I, and is equal to 1.96, with a potency of 80% corresponding to the error type II, and is equal to 0.84, a standard deviation for the 6.4 points increase in score OSDI, with an expected difference of at least 6.1 points, was considered.

Based on the above, the result was 34 patients, which increased 20% in consideration of the losses, with a total of 41 patients per group, with total study population of 123 subjects (246 eyes).

### 13.3 Schirmer

The sample size was calculated according to the formula for continuous quantitative variables:

With a statistical confidence level of 95%, which corresponds to the error type I, and is equal to 1.96, with a potency of 80% corresponding to the error type II, and is equal to 0.84, a standard deviation for the 1.72 mm/5 min increase in the Schirmer test, with an expected difference of at least 0.13 mm/5 min, was considered.

Based on the above, the result was 80 patients, which increased 20% in consideration of the losses, with a total of 96 patients per group, with total study population of 288 subjects (576 eyes).

Based on the above calculations and considering the primary outcome variable, and Schirmer test used in the study to demonstrate efficacy between the 3 groups, the total population to evaluate will be of 288 subjects.

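### The section 13 sample sizes do not follow from their printed formula and inputs; Schirmer, which sets the total of 288, works out at about 2,745 per group, not 80

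*Combined protocol and SAP*

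**What the plan says.** Section 13 of the combined protocol and SAP makes three calculations, for TBUT, OSDI and Schirmer, and adopts the largest: "The variable is considered the largest number of subjects obtained as the sample size required to meet the objectives of the study". One formula for comparing two means is displayed in section 13.1. Sections 13.2 and 13.3 name the same formula, and all three use 1.96 for 95% confidence and 0.84 for 80% power.

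- **TBUT (13.1):** SD 1.1 s, "with an expected difference of at least 0.15 seconds"; "the result was 32 patients per group, which increased 20% in consideration of the losses".
- **OSDI (13.2):** SD 6.4 points, "with an expected difference of at least 6.1 points"; the stated result is 34, raised to 41 per group.
- **Schirmer (13.3):** "a standard deviation for the 1.72 mm/5 min" increase, "with an expected difference of at least 0.13 mm/5 min, was considered"; "the result was 80 patients, which increased 20% in consideration of the losses, with a total of 96 patients per group".

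Section 13.3 then fixes the total at 288, "considering the primary outcome variable, and Schirmer test used in the study to demonstrate efficacy between the 3 groups". Section 7.2 enrols that number.

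**The concern.** A Schirmer difference of 0.13 mm against an SD of 1.72 mm is a standardised difference of 0.13/1.72 = 0.076. No conventional calculation detects that with 80 per group. The TBUT ratio is similarly small (0.15/1.1 = 0.136), yet the stated size is only 32. The OSDI ratio is large (6.1/6.4 = 0.95), yet its stated size, 34, is slightly above the TBUT one. The order of the three results does not follow the order of the inputs.

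The figure that looks wrong is the one that sets the size of the trial. If the printed inputs are the intended ones, the 80% power claim fails, and a null Schirmer result could be misread as ruling out a 0.13 mm difference that the trial had little chance of detecting. If an input is misprinted, the reader cannot tell what between-group difference the trial is built to detect.

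**Working it through.** **Inputs.** Section 13.1 to 13.3: Z values 1.96 and 0.84; SDs 1.1 s, 6.4 points and 1.72 mm; differences 0.15 s, 6.1 points and 0.13 mm; stated n per group before losses 32, 34 and 80.

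**Loss step.** This part reproduces for Schirmer: 80 × 1.2 = 96, and 96 × 3 = 288. The failure lies before it.

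**Formula step.** n per group = 2[(1.96 + 0.84) × SD / d]², rounded up.

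- Schirmer: 2 × (2.8 × 1.72 / 0.13)² = 2,744.8, so 2,745.
- TBUT: 2 × (2.8 × 1.1 / 0.15)² = 843.2, so 844.
- OSDI: 2 × (2.8 × 6.4 / 6.1)² = 17.26, so 18.

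The printed formula subtracts the Z values. Taken literally, 1.96 − 0.84 = 1.12:

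| Variable | Stated n | Z values added | Z values subtracted | Added / stated |
|---|---|---|---|---|
| Schirmer | 80 | 2,745 | 440 | 34 |
| TBUT | 32 | 844 | 135 | 26 |
| OSDI | 34 | 18 | 3 | 0.5 |

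For Schirmer, none of these standard variants gives 80: one-sided alpha (2,162), one-sample (1,373), eyes as the unit (1,373), or the SD read as a variance (1,596).

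**Power on the printed inputs** (two-group t test, two-sided 0.05):

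- Schirmer, d = 0.13 mm: 7.6% at 80 per group; 8.2% at 96, that is, with no losses; 10.3% if 160 eyes per group counted as fully independent.
- TBUT, d = 0.15 s: 13.7% at 80 per group.
- OSDI, d = 6.1 points: over 99.9% at 80 per group; 97% at the stated 34.

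**What the stated sizes would imply.** Solving the formula for d, with d = 2.8 × SD × √(2/n), or for SD, with SD = d / [2.8 × √(2/n)]:

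- Schirmer, n = 80: d = 0.76 mm if the SD is right, or SD = 0.29 mm if the difference is right.
- TBUT, n = 32: d = 0.77 s, or SD = 0.21 s.
- OSDI, n = 34: d = 4.35 points, or SD = 8.98 points.

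The wording of 13.3 leaves open whether 1.72 is the SD or the increase. If it were the increase, n = 80 would need an SD of 1.72 / [2.8 × √(2/80)] = 3.9 mm, a figure the documents do not give.

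**Detectable difference at 80 evaluable per group**, if the SDs stand (80% power, two-sided 0.05; formula, then t test): Schirmer 0.761 and 0.767 mm; TBUT 0.487 and 0.490 s; OSDI 2.83 and 2.85 points. With alpha halved for two comparators, Schirmer becomes 0.838 and 0.845 mm.

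**The case against.** The strongest objection is that only non-reproducibility is proven, not a shortage of patients. The 2,745 and the 8% depend on 1.72 and 0.13 mm being the intended inputs, and other readings exist. OSDI's 34 is close to a two-group total (2 × 17.26 = 34.5). If all three stated sizes are two-group totals, Schirmer 80 implies d = 1.08 mm, which is 13% of 8.3 mm, and TBUT 32 implies d = 1.09 s, which is 15% of 7.3 s. Both baselines fall inside the eligibility ranges in section 12.1. So one combined reading, with 0.13 and 0.15 taken as proportions of baseline, would fit all three figures.

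This stands as a reason to check the inputs before concluding that the trial is underpowered. It does not rescue the text: section 13 prints absolute units, and 34 is carried forward to 41 per group. The section is wrong as written on that reading too.

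Three smaller points are fair:

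- The subtraction is harmless if the power value was meant as −0.84. That would restore 2.80, and with it 2,745, 844 and 18.
- Losing 20% of 96 leaves 77 rather than 80, but this moves the detectable Schirmer difference only from 0.77 to 0.78 mm.
- The power figures are for one pairwise comparison of means. Section 15 plans ANOVA across the groups, and section 14.1 judges efficacy by a responder rule. The 7.6% is therefore not the chance of meeting that rule. It is the right comparison for section 13, which uses the pairwise formula.

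**Conclusion.** The point holds. None of the three sample sizes in section 13 follows from its printed formula and inputs, with the Z values added or subtracted, and the errors run in both directions. For Schirmer, which sets the 288, the printed inputs require 2,745 per group against 80 stated, and 80 per group gives about 8% power against the 80% claimed.

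These sizes assume that 1.72 mm is the SD, that 0.13 mm is an absolute between-group difference, and that two groups are compared at two-sided 0.05. The documents do not show which figure is at fault, so this is not proof that the trial is too small. It does show that the stated justification for 288 cannot stand as written and must be corrected.

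**What to change.** 1. Print the formula with the two Z values added.
2. Check each SD and difference against its cited source. State which figure is the SD, and whether each difference is absolute or a proportion of baseline.
3. If an input or unit was misprinted, correct it and show the recalculation for all three variables, labelled per group or in total.
4. If the SDs stand, keep 288 and replace the 0.13 mm and 0.15 s power claims with a statement such as: *With 80 evaluable subjects per group and two-sided alpha of 0.05, the study has 80% power for a pairwise between-group difference of about 0.77 mm/5 min in Schirmer, 0.49 s in TBUT and 2.9 points in OSDI.* If alpha is split over the two comparators, the Schirmer figure is about 0.84 mm by the formula (0.845 by t test). Correct the OSDI requirement to 18 per group by the formula (19 by t test).
5. Add a sentence on why 0.77 mm is a relevant target. The rise of more than 30% in section 14.1.2 equals 1.2 to 4.2 mm for baselines of 4 to 14 mm. It is a within-subject change and does not by itself justify a between-group difference.

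The cost is a check of three cited sources and a rewrite of section 13, with no extra patients if the SDs stand. The downside is that the declared detectable Schirmer difference becomes about six times the 0.13 mm now claimed (0.77 / 0.13 = 5.9).
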